# 3.2.1.1.3 Exploratory efficacy analysis of the primary efficacy endpoint

The percentage of responder subjects at Week 6 after the second injection between the upper limb and the lower limb as primary TT will be analysed on the mITT population using a multivariate logistic regression model. The analysis will include the primary TT limb and country as fixed factors and the composite AROM value at

baseline as covariate. The lower limb and the Czech Republic will be defined as reference level for the primary TT limb and the country, respectively. The adjusted odds ratio for the primary TT (UL *versus* LL) and its associated two-sided 95% CI will be presented as well as the adjusted odds ratio for the country (France/Russia/USA *versus* Czech Republic). The p-values of each fixed factor of the model will also be presented.

The following SAS® code will be used:

PROC LOGISTIC data = ADFT(where = (paramcd="RESP" AND mittfl="Y" AND avisitn=6));

CLASS limb countryc;

MODEL avalc(event = "Y") = limb countryc carom\_b;

RUN;

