10.4.6 Adjustment for Country/Centre Effect

Descriptive analysis of the primary efficacy endpoint will be performed by country.

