## 1.2.1 Study population

The current study will enrol adult subjects with hemiparesis due to ABI (i.e. stroke or traumatic brain injury (TBI)), presenting with muscle overactivity impeding motor function based on the investigator's judgement, including potentially one of the following requiring botulinum neurotoxin (BoNT) treatment: typical clenched fist, flexed wrist, flexed elbow, or plantar flexed foot pattern. All subjects must have the ABI at least 12 months before the study.

It is planned to recruit approximately 155 subjects at approximately 20 sites in Europe and the USA, in order to achieve 145 evaluable subjects. Recruitment will be stratified by country to ensure that 50% of subjects have the UL as primary TT and 50% of subjects have the LL as primary TT (with  $\pm 10\%$  flexibility).

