# • AROM against 10 prespecified muscle groups, 5 in upper and 5 in lower limbs

Summary statistics (including the two-sided 95% CI) will be presented for raw values and changes from baseline at each relevant visit:

- Baseline (for raw values only),
- Week 6 and Week 12 of injection cycle 1,
- Re-injection cycle visit (Week 12 or Week 16 or Week 20 of injection cycle 1),
- Week 6 and Week 12 of injection cycle 2,
- Last study visit (including Early withdrawal visit).

For AROM against each 10 prespecified muscle group, the change from baseline between the upper limb and the lower limb as primary TT will be analysed using an analysis of covariance (ANCOVA) at each relevant postbaseline timepoint previously listed. The analysis will include the primary TT limb and country as fixed factors and the AROM value at baseline as covariate. The lower limb and the Czech Republic will be defined as reference level for the primary TT limb and the country, respectively. The adjusted mean changes from baseline for each primary TT and its associated two-sided 95% CIs will be presented. The p-values of each fixed factor of the model will also be presented.

The following SAS® code will be used:

PROC MIXED data = ADFT(where = (paramcd="ROMxx" AND ittfl="Y")) method=reml;

BY avisitn;

CLASS limb countryc;

MODEL chg = limb countryc base / DDFM=kr;

LSMEANS limb countryc / ALPHA=0.05 CL;

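### Country odds ratios, LS means and p-values come from models with no site term, so their standard errors are too small if outcomes correlate within site (minor: exploratory outputs only)

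*SAP*

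**What the plan says.** For the responder rate at Week 6 after the second injection, SAP 3.2.1.1.3 fits a logistic regression: "The analysis will include the primary TT limb and country as fixed factors and the composite AROM value at" baseline as covariate. The code lists "CLASS limb countryc" as its only classification variables. The output includes the odds ratio for limb "as well as the adjusted odds ratio for the country (France/Russia/USA *versus* Czech Republic", and then "The p-values of each fixed factor of the model will also be presented".

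The AROM analyses in SAP 3.2.1.2 use "MODEL chg = limb countryc base / DDFM=kr" followed by "LSMEANS limb countryc / ALPHA=0.05 CL". The text promises adjusted means by primary limb and a p-value for each fixed factor. The country LS means with 95% limits arise from the code, and the raw SAS output goes into the statistical appendix. The rank-based fallback has the same structure. The composite AROMs, MFS, walking speed, EQ-5D-5L and SF-12 reuse this model. For the EQ-5D-5L index, the SAP says that a reference level is chosen in order to compare France with the United States.

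On sites, SAP 1.2.1 says: "It is planned to recruit approximately 155 subjects at approximately 20 sites in Europe and the USA". SAP 3.2.6.1 lists four countries. Protocol 10.4.6, whose title covers both country and centre, says only: "Descriptive analysis of the primary efficacy endpoint will be performed by country". SAP 3.2.17 on pooling of centres likewise offers description by country. Neither supplies a site term.

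**The concern.** Country varies only between sites. The error that matters for a country contrast is therefore the variation between sites within country. With 20 sites in four countries that is 20 − 4 = 16 degrees of freedom, whereas the planned models use subject-level error with about 140. The Kenward-Roger option cannot correct this, because the code has no RANDOM or REPEATED statement and so gives it no between-site variance to work with.

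The design makes some correlation within site plausible. The study is open-label. At each site the investigator chooses the target limb and the dose split, reads the goniometer, times the second injection and scores the local MFS, and site staff teach the exercises. The lower-limb response threshold is 5° on a sum of two readings, so a small systematic reading difference between sites could move subjects across it.

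At stake is the reading of the country results: differences between a few sites may look like differences between countries. There are many such results. The single-muscle-group AROM analyses alone give 10 groups × 6 timepoints = 60 country p-values.

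**Working it through.** **Inputs from the documents.** 145 evaluable subjects, about 20 sites and four countries (SAP 1.2.1 and 3.2.6.1), and a 60% response rate estimated to ±8% with a 95% interval (SAP 1.3.4). **Assumed**, because the documents do not give them: the ICC, and equal sites of 145/20 = 7.25 subjects.

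**Step 1. The plan's own figure.** n = 1.96² × 0.60 × 0.40 / 0.08² = 144.05, rounded up to 145. Then 145/0.95 = 152.6, rounded up to 153. Both stated numbers reproduce. The documents state no error rate for the country comparison.

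**Step 2. Formula.** The design effect is DE = 1 + (7.25 − 1) × ICC. A nominal 5% test that ignores site has these false-positive rates when countries do not differ:

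- global test, 3 df: P(χ²₃ > 7.815/DE)
- one country against the reference: 2 × P(Z > 1.96/√DE)

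At ICC 0.05, DE = 1 + 6.25 × 0.05 = 1.31. The χ² cut-off becomes 7.815/1.3125 = 5.95, giving 11.4%. The Z cut-off becomes 1.96/√1.3125 = 1.71, giving 8.7%.

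| ICC | DE | Global test | One country vs reference |
|---|---|---|---|
| 0 | 1.00 | 5.0% | 5.0% |
| 0.01 | 1.06 | 6.1% | 5.7% |
| 0.02 | 1.12 | 7.4% | 6.5% |
| 0.05 | 1.31 | 11.4% | 8.7% |
| 0.10 | 1.62 | 18.6% | 12.4% |
| 0.20 | 2.25 | 32.4% | 19.1% |

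**Step 3. Simulation of the planned models.** 3,000 trials per setting, 20 sites in four countries, no true country effect, and limb, country and baseline in the model.

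- Logistic model, global test, equal sites: 10.4% at ICC 0.05, 16.5% at 0.10 and 31.0% at 0.20.
- Logistic model, global test, unequal sites (2 to 16 subjects; 9, 3, 4 and 4 sites per country): 11.8%, 21.1% and 38.3%.
- ANCOVA, global test, over both site patterns: 11.1% to 14.6% at ICC 0.05, and 19.5% to 21.7% at 0.10.
- Upper-versus-lower-limb contrast in the logistic model, with limb varying within site: 4.3% to 5.8% throughout, so no inflation.

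**Step 4. Does a site-based error term repair it?** An F test on the 20 site means (3 and 16 df) stays at 4.1% to 5.7% for every ICC from 0 to 0.30. In a balanced simulation with continuous outcomes, a random site effect holds the country test at 3% to 6%, counting the fits where the site variance is estimated as zero and the model reverts to the planned one.

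**The case against.** The strongest reply is that nothing rests on these results. Protocol 10.3 and SAP 3.1.5 rule out formal testing and call any p-value exploratory. No study objective compares countries. The models are introduced as comparisons between upper and lower limb as primary target. In SAP 3.2.1.1.3 the stated confidence interval attaches to the limb odds ratio, and the ANCOVA text names adjusted means by limb only. This stands, and it is why the priority is low. It does not remove the point: country odds ratios and country p-values are explicitly planned, and an exploratory p-value or interval still needs the right error term.

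A reader might infer more than the documents support:

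- **That country differences will be false positives two to three times too often.** This depends on an ICC that the documents do not give. On the formula above, 10% to 15% needs an ICC of about 0.04 to 0.075 for the global test, or about 0.07 to 0.14 for a single country contrast. At 0.02 or below the inflation is at most about 1.5-fold.
- **That the limb comparison is compromised because the 50:50 split is controlled only at country level.** Nothing says that sites recruit one limb only, and the simulation shows no inflation when limb varies within site.
- **That centre is ignored altogether.** Disposition is tabulated by centre. It is the efficacy models that omit it.

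The repair can also be questioned for the binary outcome. With about seven subjects per site, a mixed logistic model estimates the site variance poorly, and no such model was tested here. This stands too, and the fix treats the logistic model differently for that reason.

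**Conclusion.** The point holds in a limited, conditional form. The planned country odds ratios, LS means and p-values use subject-level error for a factor that varies only between sites. With any positive within-site correlation they will look more precise than they are.

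The size cannot be fixed from the documents. For ICCs from 0 to 0.20 the false-positive rate of the global country test runs from 5% to about 32% with equal sites, and somewhat higher in the unequal pattern simulated. What is inflated is the chance of p < 0.05 when countries do not differ; it does not follow that any particular reported difference is false. The primary analysis in SAP 3.2.1.1.1 is a single proportion with its interval and no country term, so it is untouched by this point. Priority: minor.

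**What to change.** In the PROC MIXED code of SAP 3.2.1.2, in both the main and the rank-based version, add the site identifier to CLASS and the statement `RANDOM siteid(countryc);`. The Kenward-Roger option then uses between-site error for country. The analyses that reuse this model inherit the change.

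For the logistic model in SAP 3.2.1.1.3, and anywhere the sponsor prefers not to alter the model, keep country as an adjustment factor only. Remove the country odds ratios, LS means and p-values, and show country results descriptively, as Protocol 10.4.6 and SAP 3.2.17 already provide.

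Protocol 10.4.5 specifies these models, so record the change in SAP section 5.

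The cost is small: one statement per procedure, or deleted output, with centre already recorded. Country limits will be wider. For some outcomes the site variance may be estimated as zero, which returns the planned model.

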## 3.2.1.2 Secondary efficacy analyses

The analyses of the secondary efficacy endpoints will be performed on the ITT population.

Percentage of responder subjects at Week 6 after the first injection, according to composite AROM in the primary TT limb

A frequency table of the percentage of responder subjects at Week 6 after the first injection will be provided with the two-sided 95% CI. Subjects with missing responder status at Week 6 after the first injection will be considered nonresponders. The number of missing data will be provided.

# • AROM against 10 prespecified muscle groups, 5 in upper and 5 in lower limbs

Summary statistics (including the two-sided 95% CI) will be presented for raw values and changes from baseline at each relevant visit:

- Baseline (for raw values only),
- Week 6 and Week 12 of injection cycle 1,
- Re-injection cycle visit (Week 12 or Week 16 or Week 20 of injection cycle 1),
- Week 6 and Week 12 of injection cycle 2,
- Last study visit (including Early withdrawal visit).

For AROM against each 10 prespecified muscle group, the change from baseline between the upper limb and the lower limb as primary TT will be analysed using an analysis of covariance (ANCOVA) at each relevant postbaseline timepoint previously listed. The analysis will include the primary TT limb and country as fixed factors and the AROM value at baseline as covariate. The lower limb and the Czech Republic will be defined as reference level for the primary TT limb and the country, respectively. The adjusted mean changes from baseline for each primary TT and its associated two-sided 95% CIs will be presented. The p-values of each fixed factor of the model will also be presented.

The following SAS® code will be used:

PROC MIXED data = ADFT(where = (paramcd="ROMxx" AND ittfl="Y")) method=reml;

BY avisitn;

CLASS limb countryc;

MODEL chg = limb countryc base / DDFM=kr;

LSMEANS limb countryc / ALPHA=0.05 CL;

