4 SELECTION AND WITHDRAWAL OF SUBJECTS

4.1 Inclusion Criteria

All subjects must fulfil all of following criteria to be included in the study:

- (1) Subjects aged at least the national legal adult age.
- (2) Subjects with hemiparesis due to ABI (i.e. stroke or Traumatic Brain Injury (TBI)) presenting with muscle overactivity impeding motor function based on investigator's judgement including, but not limited to, at least one of the following requiring BoNT treatment: typical clenched fist; flexed wrist; flexed elbow; or plantar flexed foot.
- (3) At least 12 months since the ABI.
- (4) Naïve or non-naïve to BoNT treatment; if non-naïve, at least 4 months after the last BoNT injection, of any serotype.
- (5) Upper limb active function with an overall score between 2 and 7, as assessed by MFS locally rated score, if the primary TT limb is the UL.
- (6) A 10-metre maximal WS barefoot between 0.2 and 1.4 m/s, if the primary TT limb is the LL. Maximal WS barefoot will be performed preferably without walking aids. However, a cane may be permitted if absolutely necessary (although this may prevent detection of treatment-induced improvements). In this case, the same aid will have to be used for all WS assessments during the study.
- (7) Subjects must provide written informed consent to participate in the study prior to any study-related procedures.
- (8) Female subjects of childbearing potential (not surgically sterile or 2 years postmenopausal) must use a medically accepted method of contraception and must agree to continue use of this method for the duration of the study until the last visit of the subjects and for at least 12 weeks post injection. Acceptable methods of contraception include total abstinence, male partner has had a vasectomy, double barrier method (e.g. male condom plus spermicide, or female diaphragm plus spermicide), intrauterine device, or hormonal contraceptive (oral, transdermal, implanted and injected)..
- (9) Subjects must be willing and able to comply with study restrictions and to remain at the clinic for the required duration during the study period and willing to return to the clinic for the follow-up evaluation as specified in the protocol.

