6.1.2 Second Study Therapy: GSC

At the first visit, the investigator will prescribe the rehabilitation programme for the GSC [12]. The GSC is a motivational tool, which will be described in detail in the Study Operational Manual. The physiotherapist will teach each subject the stretching postures and exercises to perform on a daily basis throughout the study. These will be tailored to the individual subject's needs and will form the GSC therapy. The main focus will be on the primary TT limb (as determined at the Baseline Visit) and then the other limb. All muscle groups requiring active training and/or stretching should be trained.

The subjects will be given a diary at the Baseline Visit. As part of the GSC, they will be asked to record in this diary each day whether they have performed the GSC therapy. A copy of the diary and details regarding diary completion will be provided in the Study Operational Manual.

Telephone calls will be made to the subjects every 2 weeks to encourage them, check the GSC therapy is being performed daily and that they are completing the diary. The exercises may be adjusted at study visits, based on the clinical judgement of the investigator or physiotherapist.

At each postbaseline FU visit, the subjects will return the diary. The investigator will count the number of days when GSC therapy was not performed and will record this in the eCRF.

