# 3.1.5 Significance testing and estimation

The statistical analysis of efficacy is only descriptive therefore no formal statistical significance testing will be performed and all the analyses will be primarily descriptive in nature. When appropriate and unless otherwise specified, two-sided 95% CIs will be displayed and if p-values are presented, they will be for exploratory purposes only. For the 95%CIs of proportions, the Agresti-Coull interval will be used.

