# Composite AROM against injected muscle groups (any of the 10 prespecified), in upper and lower limbs

Summary statistics (including the two-sided 95% CI) will be presented for raw values and changes from baseline at each relevant visit: baseline (for raw values only), Week 6 and Week 12 of injection cycle 1, re-injection cycle visit, Week 6 and Week 12 of injection cycle 2, and last study visit.

The change from baseline of composite AROM against each injected muscle group between the upper limb and the lower limb as primary TT will be analysed in the same way as AROM against 10 prespecified muscle groups.

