# • Active UL function

Summary statistics (including the two-sided 95% CI) will be presented overall and by primary TT limb for raw values of the MFS overall scores, assessed locally and centrally by a reviewer blinded regarding the order of the video recording/visit number for a given subject, at baseline, Week 12 of each injection cycle and last study visit, as well as for the change from baseline at Week 12 of each injection cycle and last study visit.

For the MFS overall scores, assessed locally and centrally by a reviewer blinded, the change from baseline between the upper limb and the lower limb as primary TT will be analysed at Week 12 of each injection cycle and last study visit using the same model as AROM against 10 prespecified muscle groups.

The concordance between the results from the local assessment by the investigators and from the central review will be evaluated. For each analysed visit, the Lin's concordance correlation coefficient [9] and the associated two-sided 95% CI will be calculated on the raw data. The Brand-Altman graph will also be presented.

The Lin's concordance correlation coefficient and the associated two-sided 95% CI will be calculated using the macro mccc.sas (http://bioinformaticstools.mayo.edu/research/mccc/).

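### The secondary ANCOVA takes separate 95% CIs for UL-target and LL-target subjects from one pooled residual variance, so they are miscalibrated if the two groups' spread of change differs

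*SAP*

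**What the plan says.** SAP section 3.2.1.2 (AROM against 10 prespecified muscle groups) regresses change from baseline on primary TT limb, country and baseline value, separately at each visit: "MODEL chg = limb countryc base / DDFM=kr". Limb-specific means and limits come from "LSMEANS limb countryc / ALPHA=0.05 CL", and the text adds that "The adjusted mean changes from baseline for each primary TT and its associated two-sided 95% CIs will be presented". There is no REPEATED statement. The parts on composite AROM, full composite AROM, active UL function, active LL function and quality of life all refer back to this model.

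The plan leaves the parametric model for two reasons only: gross non-normality, judged on the change from baseline overall, or failure to converge. The replacement is the same model on ranks, again with one residual variance.

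The unadjusted summaries are not uniform. For MFS, "Summary statistics (including the two-sided 95% CI) will be presented overall and by primary TT limb for raw values of the MFS overall scores", with change from baseline treated the same way, and walking speed follows the same pattern. For composite AROM the summary statistics "will be presented for raw values and changes from baseline at each relevant visit: baseline (for raw values only"), followed by the later visits, with no split by limb. The single-muscle and full composite AROM summaries are likewise unsplit. SAP section 3.2.20 breaks AROM down by primary TT limb at baseline only.

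On the status of the estimates, SAP section 3.1.5 says that "two-sided 95% CIs will be displayed and if p-values are presented, they will be for exploratory purposes only".

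**The concern.** A per-group interval built on a pooled variance is right only if the groups share that variance. `DDFM=kr` adjusts degrees of freedom and standard errors within the specified covariance structure; it does not relax the equal-variance assumption. The documents give three reasons to doubt equality here.

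- **Permitted dose range.** Protocol sections 3.1 and 6.1.1 fix 1500 U in total, at least 750 U in the primary TT limb, at most 1000 U in the UL, and some dose in the UL. UL-target subjects can therefore receive 750–1000 U in the UL and 500–750 U in the LL, each range 250 U wide. LL-target subjects can receive 750 to under 1500 U in the LL and more than 0 to 750 U in the UL, each range about 750 U wide. These are permitted ranges; actual doses may cluster.
- **Rehabilitation.** Protocol section 6.1.2: "The main focus will be on the primary TT limb (as determined at the Baseline Visit) and then the other limb".
- **Entry limits.** Protocol section 4.1 requires an "overall score between 2 and 7, as assessed by MFS locally rated score, if the primary TT limb is the UL", and a walking speed of 0.2–1.4 m/s only if the LL is the target. A zero distance and time is scored as 0 m/s (SAP Appendix 1, item 8), so a floor in walking speed is possible among UL-target subjects, who have no entry limit on it.

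In a descriptive study the intervals are what a reader uses to judge precision. For AROM change no unadjusted by-limb SD or CI would reveal a difference in spread.

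**Working it through.** **Plan's own figure.** The ANCOVA has none. The sample size supplies N: 1.96² × 0.6 × 0.4 / 0.08² = 144.05, rounded up to 145; 145 / 0.95 = 152.6, rounded up to 153. Both match Protocol section 10.2.

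**Inputs.** N = 145 is used for the ANCOVA. The SAP runs the secondary analyses on the ITT population, so actual numbers will vary by visit; coverage depends mainly on the split and the SD ratio. A 50:50 split gives 73 and 72 subjects; the ±10% flexibility allows 87 and 58. The ratio r of the larger to the smaller residual SD is not in the documents, so 1 to 2 is assumed as a range.

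**Formulas.** With the smaller SD set to 1:

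- pooled SD: s_p = √{[(n₁−1)·1 + (n₂−1)·r²] / (N−2)}, where group 2 is the more variable
- interval width relative to the correct width: s_p for the less variable group, s_p / r for the more variable group
- approximate coverage: 2Φ(t × relative width) − 1, with t = 1.977 on N − 6 = 139 df

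Combining a t multiplier with the normal distribution gives 95.2% rather than 95.0% at r = 1.

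**Worked case, 50:50 and r = 1.5.** s_p = √[(72 + 71 × 2.25) / 143] = √1.6206 = 1.273. Relative widths are 1.27 (less variable) and 1.273 / 1.5 = 0.85 (more variable). Coverage is 98.8% and 90.7%.

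**Coverage of the nominal 95% CI, more variable / less variable group:**

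| Split | r = 1 | r = 1.25 | r = 1.5 | r = 2 |
|---|---|---|---|---|
| 50:50 | 95.2 / 95.2 | 92.6 / 97.5 | 90.7 / 98.8 | 88.1 / 99.8 |
| 60:40, smaller group more variable | 95.2 / 95.2 | 92.0 / 97.1 | 89.3 / 98.4 | 85.7 / 99.7 |
| 60:40, larger group more variable | 95.2 / 95.2 | 93.3 / 97.8 | 91.9 / 99.1 | 90.2 / 99.9 |

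**Check by simulation.** The model with limb, a four-level country factor (assumed shares 35/30/20/15%) and baseline was simulated 4000 times per setting. At 50:50 and r = 1.5 coverage was 90.4% / 98.2%. At r = 2 the more variable group had 89.7% (50:50), 86.6% (60:40, smaller group more variable) and 91.3% (60:40, larger group more variable), about one to one and a half points above the formula.

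**With a separate variance per limb.** Coverage was 94.3% to 96.0% for both groups in every setting. This used an iterated weighted fit that approximates the SAS model. At r = 1 and 50:50, mean interval width went from 0.482 to 0.485 in one group and from 0.485 to 0.488 in the other; the largest increase at any split was 0.539 to 0.545, about 1%.

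**Limb comparison.** With no true difference, the pooled model's rejection rate was 4.7% to 5.7% at 50:50. At 60:40 and r = 2 it was 8.3% (smaller group more variable) or 2.5% (larger group more variable); a separate variance per limb gave 4.9% in both.

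**The case against.** The best defence is that nothing in the documents shows the variances to be unequal. Different doses and rehabilitation focus predict different mean changes, which the limb term absorbs. The entry limits restrict baseline, which is a covariate. A common-variance ANCOVA is the ordinary reading of the model named in Protocol section 10.4.5.2, and the comparison between limbs is robust at 50:50. For MFS and walking speed, each group's own spread and CI are already tabulated. SAP section 3.2.1.2 also commits to filing the model-checking output.

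Much of this stands. A reader might infer that one limb's interval is certainly wrong. The documents do not support that: with equal SDs both intervals are correct. Nor can one say which group is affected, and this could vary by muscle group and visit.

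A reader might also infer that the primary result is compromised. It is not: the responder proportion uses an Agresti-Coull interval (SAP section 3.1.5), and its by-limb description (section 3.2.20) does not use this model. Nor is it established that the ANCOVA covers the composite behind the primary endpoint. Section 3.2.1.2 names composite AROM against injected muscle groups, whereas section 3.1.1 defines the primary composite regardless of injection.

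What the defence does not answer is that the plan relies on an assumption its own design makes doubtful. Filing diagnostics leads to no action when variances differ, and for AROM change there is no by-limb table to fall back on.

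**Conclusion.** The point holds conditionally. The per-limb intervals assume equal residual variance, no planned step responds if that fails, and the design gives reason to think it may. At an SD ratio of 1 there is no error. At 1.25 coverage is off by about 2 to 3 points. At 1.5 to 2 the more variable group's coverage is about 86% to 92% by the formula, depending on the split, while the other group's interval is needlessly wide. These figures rest on assumed ratios, N = 145 and the splits allowed by the recruitment rule. The effect is confined to secondary, descriptive estimates and matters most for AROM change, where the model-based CI is the only by-limb interval planned. This is a cheap improvement to make, not a flaw in the primary analysis.

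**What to change.** Two changes to SAP section 3.2.1.2:

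1. Add `REPEATED / GROUP=limb;` to the PROC MIXED call for AROM and for every endpoint that reuses the model. Limb is already in the CLASS statement and `DDFM=kr` is already set. The rank fallback repeats the same model, so it should carry the statement too. The fixed effects named in the protocol do not change.
2. Present the change summaries for single-muscle, composite and full composite AROM by primary TT limb as well as overall, with each group's own SD and 95% CI, as is already done for MFS and walking speed.

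The cost is one SAS statement per call, extra table rows, and intervals about 1% wider if the variances turn out equal.
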